**Specific Aim 2:** Evaluate whether increases in cardiovascular fitness mediate cognitive improvement. Cardiovascular fitness will be estimated with a reliable and valid measure of oxygen uptake (VO2max) prior to and after 12 weeks of the AE vs. CONT intervention and at 8 weeks *post-training follow up*. Estimated VO2max is the most appropriate test as it accounts for initial fitness level of the participant without the physically exhausting and frightening experience of a full VO2max test. We predict that estimated VO2max improvement in the AE group will predict cognitive gain with training at 12 weeks and 8 weeks *post-training follow up*.

**Specific Aim 3:** Compare changes in measures of everyday functional abilities (U. California San Diego Performance-Based Skills Assessment, UPSA) in the AE vs. CONT training groups. We predict that the AE group will show greater gains in the UPSA than CONTs at 12 weeks and 8 weeks *post-training follow up*.

Improvements in cognitive function and skills of everyday living in SCZ are highly resistant to treatment with our current choices of medications. SCZ is generally a life-long condition: thus the disabilities with which these patients struggle will require treatment from the VA for the life of the patients. If AE leads to enhanced cognitive

functioning of these patients in everyday activities, AE could become a valuable treatment modality for the rehabilitation of SCZ patients, having dual benefits on both cognition and physical health. Hence this proposal is highly relevant to the VA mission of reducing impairments and rehabilitating our patients.

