#### **(2) Secondary outcome measures:**

**a.** To confirm the cardiovascular effects in the AE group we will perform an exercise test on all participants. Cardiovascular fitness will be estimated by the YMCA sub-maximal cycling protocol at Baseline, *Endpoint (12 weeks), and at 8 weeks post-training follow up*. Estimated **VO2max** is the most appropriate test as it accounts for initial fitness level of the participant without the physically exhausting and frightening experience of a full V0max test. This is particularly critical since our population will be sedentary. This test uses an "extrapolation" method in which heart rate (HR) workload values are obtained at 4 points and extrapolated to predict workload at the estimated maximum HR (MHR) (e.g. 220 minus age in years). VO2max is then calculated from the predicted maximum workload. Participants will be asked to ride a stationary bicycle for 4 three-minute stages. The first stage is a warm-up at 50 revolutions per minute (RPM) at a power level of 25 watts. During all testing stages, HR will be continuously monitored and will not exceed 85% of age-predicted maximum HR. Average HR during the final 30 seconds of the 2nd and 3rd minutes will be plotted against workload. Three-minute trial workloads will be chosen based on the participants' HR at the end of the warm-up period. The fourth 3-minute stage will be a cool down period at the end of the test. Participants will be allowed to stop the test at anytime if they feel faint, dizzy, short of breath, or for any other reason.

**b.** Ultimately, the goal of AE for cognitive remediation is to help our patients achieve improvements in real-world functioning and psychiatric stability. The U. California San Diego Performance-Based skills assessment (**UPSA**) is a measure of functional ability that can detect immediate improvements in the ability to carry out functionally meaningful tasks (Patterson et al. 2001; Harvey et al. 2007). It has excellent test-retest reliability (Leifker et al. 2010) and is able to quantify the potential for functional improvement with cognitive change (Green et al. 2011). As such, the UPSA is an excellent predictor of real-world functional outcomes (Mausbach et al. 2008; see Leifker et al. 2011 for a review). This literature supports our plan to use this measure in **SA3** at Baseline, *Endpoint (20 weeks), and 8 weeks post-training follow up*.

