**Specific Aim 3:** Compare changes in performance-based measurement of functional abilities (by the UPSA) in the AE vs. CONT training groups. We predict that the AE group will have greater improvement in the UPSA than the CONT group at the end of treatment and at three months follow up.

**Statistical analysis:** The statistical approach for Spec Aim 3 will be similar to that of Spec Aim 1. Descriptive statistics will be generated with 95% confidence that our sample-based estimates will be within 0.20 SD of the population values. Hypotheses will be tested (and effect size estimates will be generated) with a univariate ANCOVA looking at change scores with baseline measures plus age, sex, and anticholinergic load as covariates. With a total sample size of 20 participants per group we will be sensitive to an effect size in UPSA scores of  $f=0.481$  (alpha=0.05: power=0.80). This power and effect size will enable us to detect changes in UPSA scores of about 14%, a clinically meaningful change. A similar analysis (with identical sensitivity) will be used to assess the stability of the treatment effect through a univariate ANCOVA of change scores between the post-treatment and 3 month follow up measurements with post-treatment scores used as the covariate.

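### The Aim 3 durability ANCOVA adjusts for the week-12 UPSA score, a post-randomisation variable, and so understates any fading of the effect; it also refers to a 3-month visit that is not scheduled

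*Combined protocol and SAP*

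**What the plan says.** The statistical analysis plan for Specific Aim 3 predicts that AE will show "greater improvement in the UPSA than the CONT group at the end of treatment and at three months follow up". The main Aim 3 model is an ANCOVA of UPSA change adjusted for baseline score, age, sex and anticholinergic load, with 20 participants per group. It is said to be able to "detect changes in UPSA scores of about 14%, a clinically meaningful change".

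Durability has its own model: "A similar analysis (with identical sensitivity) will be used to assess the stability of the treatment effect". Its outcome and covariate are "change scores between the post-treatment and 3 month follow up measurements with post-treatment scores used as the covariate".

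The visit times differ between sections:

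- **Specific Aim 3 on the aims page:** "greater gains in the UPSA than CONTs at 12 weeks and 8 weeks" after training.
- **Secondary outcome a (VO2max):** "Endpoint (12 weeks), and at 8 weeks post-training follow up".
- **Secondary outcomes b (UPSA) and c (MCCB domains):** "Endpoint (20 weeks), and 8 weeks post-training follow up".
- **Schedule table:** Endpoint at Day 84 and one later visit, at 20 weeks, labelled as the 8-week follow-up. The UPSA is marked at both.
- **Aim 3 analysis text:** three months.

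**The concern.** Adjusting the 12-week change for the baseline score is sound, because randomisation balances baseline in expectation. That argument does not carry over to the week-12 score, which contains the treatment effect under study. Adjusting for it compares AE and CONT participants who have the same week-12 score. If AE works, these participants come from different parts of their arms' distributions, and the CONT members of the comparison are expected to fall back further towards their own arm's mean. AE then appears to hold up better than it does.

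At stake is the estimate of durability. The Aim 2 analysis text describes the pilot's analyses as aimed at effect sizes for later studies, and the sample size section gives the same purpose. A durability estimate tilted towards persistence would pass into the planning of the follow-on trial, and a larger sample would not remove the tilt.

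Separately, an analyst following the Aim 3 text would look for a visit that does not exist. With the endpoint labelled as both 12 and 20 weeks, the two scores to be subtracted are not identified consistently.

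**Working it through.** **The plan's own figure.** The Aim 3 text gives a detectable f of 0.481, and says the durability analysis has the same sensitivity. With N = 40, four covariates (34 error df), two-sided alpha 0.05 and power 0.80, the noncentral F gives f = 0.456, which is the Aim 1 figure. At f = 0.481 the power is 0.84. So 0.481 does not reproduce for 20 per group. Nothing below depends on this.

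**What the planned coefficient estimates.** Let P and F be the week-12 and follow-up UPSA scores. Within each arm, F has slope b on P, so F − P has slope b − 1. The arm coefficient, adjusted for P, is

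(dF − dP) − (b − 1)·dP = dF − b·dP.

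The target is dF − dP, so the bias is (1 − b)·dP.

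**Inputs.**

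- n = 20 per arm (Aim 3 analysis text).
- b is not in the documents. I assume 0.8, with range 0.6 to 0.9. The UPSA description says "It has excellent test-retest reliability" but gives no figure; that points to the upper part of the range.
- dP is taken two ways: the plan's own 14%, read as an arm difference; and 0.5 SD, borrowed from the MCCB planning value in the sample size section. These are alternative sizes, not the same effect on two scales.

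**Size of the bias.**

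| b | Share of week-12 effect | If dP = 14% | If dP = 0.5 SD |
|---|---|---|---|
| 0.9 | 10% | 1.4 points | 0.05 SD |
| 0.8 | 20% | 2.8 points | 0.10 SD |
| 0.6 | 40% | 5.6 points | 0.20 SD |

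**Standard errors, dP = 0.5 SD, unit SDs.** Let k = √(2/20) = 0.316.

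- Planned model: k·√(1 − b²)·√(1 + (dP/2)²). At b = 0.8 this is 0.316 × 0.6 × 1.03 = 0.196 (simulated 0.198).
- Week-12 covariate replaced by baseline UPSA: k·√(2(1 − b)). At b = 0.8 this is 0.316 × 0.632 = 0.200 (simulated 0.202).

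**Simulation.** 10,000 trials per case, unit SDs, a common correlation b among baseline, week 12 and follow-up, and dP = 0.5 SD. Mean estimates at b = 0.8:

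| Fraction of effect kept | True dF − dP | Planned model | Baseline-adjusted model |
|---|---|---|---|
| 1 | 0 | +0.10 | 0.00 |
| 0.9 | −0.05 | +0.05 | −0.05 |
| 0.8 | −0.10 | 0.00 | −0.10 |
| 0.5 | −0.25 | −0.15 | −0.25 |
| 0 | −0.50 | −0.40 | −0.50 |

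A fully kept effect reads as further gain, and an effect kept at fraction b reads as perfectly stable. Larger losses show as losses but are understated. The sign is wrong only for kept fractions between b and 1.

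| | b = 0.9 | b = 0.8 | b = 0.6 |
|---|---|---|---|
| Coverage of planned 95% CI | 94% | 92% | 88–89% |
| Significant further gain when effect is fully kept (2.5% expected) | 5% | 7% | 11% |
| Power to show complete loss, planned | 86% | 50% | 20% |
| Power to show complete loss, baseline-adjusted | 92% | 67% | 41% |

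At b = 0.8 the power to show a halved effect is 11% planned and 22% baseline-adjusted.

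**If dP equals the plan's detectable effect.** With d = 2 × 0.481 = 0.962 and b = 0.8, the bias is 0.2 × 0.962 = 0.19 SD against a standard error of 0.21. Coverage is 86%, and a false further gain appears in 14% of trials.

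**If the durability model also keeps baseline UPSA.** The text calls it a similar analysis, so this reading is possible. Then b is the partial slope, which under a common correlation r is r/(1 + r). At r = 0.8 this is 0.44, and the bias for dP = 0.5 SD is 0.56 × 0.5 = 0.28 SD. At r = 0.9 it is 0.47, and the bias is 0.26 SD. High reliability gives no protection under this reading.

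**Timing.** Three months after a week-12 endpoint is about week 25 (12 + 13). The schedule's only post-training visit is at week 20 (12 + 8).

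**The case against.** The strongest reply is that the same section already supplies an answer. Its prediction covers both end of treatment and follow-up, and the baseline-adjusted ANCOVA can be read as applying at both. Subtracting the two arm differences gives dF − dP without the offset. That reading is fair, but the text does not state it, it yields no CI for the contrast, and the analysis labelled as the test of stability would still give the biased answer.

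The second reply is size. This is a supplementary look at a secondary outcome in a pilot of 40. At dP = 0.5 SD the bias is below one standard error, and at b = 0.9 it is 0.05 SD against 0.14. That stands, and it keeps the point short of critical.

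Third, b is a slope, not a correlation. It equals the correlation times the ratio of follow-up to week-12 SD. With correlation 0.8 and a follow-up SD 1.2 times larger, b is 0.96 and the bias nearly vanishes (0.02 SD); a smaller follow-up SD would enlarge it. This also stands: the direction requires b below 1, and the size cannot be fixed from the documents.

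The rejection and power figures matter less if the pilot is read for estimation only, but bias and coverage matter under either reading. Baseline adjustment in the replacement model adds no precision under the simulated correlations. The gain comes from dropping the week-12 covariate; keeping baseline simply matches the 12-week model. The visit labels are wording errors and add no weight to the covariate point.

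**Conclusion.** The concern holds. Followed exactly, the durability analysis estimates dF − b·dP rather than the change in treatment effect, and is biased towards persistence by (1 − b) of the week-12 effect. The form of the bias is exact for a linear model with a common slope. Its direction rests on b below 1, usual for a score measured with error, and on a positive week-12 effect, which the trial predicts. With no week-12 effect there is no bias.

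The size rests on an assumed b. For the single-covariate model as written it is 20% of the week-12 effect, with a range of 10% to 40%. At 0.5 SD and b = 0.8 this means 92% coverage and a clear loss of power to detect fading. The three-month follow-up and the 20-week endpoint label contradict the schedule whatever b is. This should be corrected before analysis; it does not touch the primary MCCB comparison.

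**What to change.** 1. **Durability.** Estimate the AE minus CONT difference in week-20 minus week-12 UPSA change, adjusted for baseline UPSA and not for the week-12 score. Report it with a 95% CI, and do not call the effect stable merely because p exceeds 0.05. At b = 0.8 the CI half-width is about 0.41 SD, so a non-significant result would be weak evidence of stability.
2. **Effect at follow-up.** State explicitly that the ANCOVA of UPSA change from baseline (baseline score, age, sex, anticholinergic load) is run at week 20 as well as week 12.
3. **Visits.** Reconcile the three-month references in the Aim 3 analysis text with the single follow-up 8 weeks after training, and the 20-week endpoint label in secondary outcomes b and c with Endpoint at Day 84.

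The cost is SAP wording: same visits, same data, same type of model. Precision is essentially unchanged at b = 0.8 (standard error 0.20 for both models) and b = 0.9 (0.14 for both). At b = 0.6 the standard error rises from 0.263 to 0.285.

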## Sample size determination

Sample size calculations for our primary outcome measure (MCCB) are based on several studies of AE compared to a control condition in which the effect sizes average approximately 0.5 (Dustman et al. 1984; Fabre et al. 2002; Heyn et al 2004; Hotting et al. 2012; Chapman et al. 2013). We also based estimated power on studies of cognitive remediation in SCZ, including a meta-analysis (Wykes et al. 2011) and studies of Posit Science computerized remediation (Fisher et al. 2010). The average effect size of the above studies is 0.5. With alpha set at 0.05, an effect size of 0.5 will yield a power of 0.80 for our **planned sample size of 20 completers per treatment group (with dropouts replaced)**. This sample size will be adequate to detect significant between group differences in MCCB change scores. More importantly for a pilot study, this sample size will allow us to estimate effect sizes specific to the target Veteran population with sufficient confidence to be useful in determining the sample size required for a future full Merit Review proposal (if indicated by the results of this pilot study). Participant retention will be an important issue. We estimate liberally from our prior work (cognitive remediation study) that *dropouts will be approximately 25%, so we will need to recruit 53 subjects in order to obtain the 40 completers needed for analysis.*

**Roles of members of the research team.** Please see delineation of roles in Budget Justification.

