### **Primary and secondary outcome measures**

#### **(1) Primary outcome measures:**

Measurement and Treatment Research to Improve Cognition in Schizophrenia Consensus Cognitive Battery (**MCCB**). The National Institute of Mental Health funded the development of a consensus battery of neurocognitive tests for use in SCZ cognitive trials. The result is the MATRICS Consensus Cognitive Battery (MCCB). It assesses seven key cognitive domains relevant SCZ: processing speed, attention/vigilance, working memory, verbal learning, visual learning, reasoning and problem solving, and social cognition. The MCCB has excellent test-retest reliability (Nuechterlein et al. 2008). It is the recommended outcome measure for SCZ cognition trials (Keefe et al. 2010). *The MCCB composite score at 12 weeks will be the primary outcome measure.*

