**Statistical analysis plan**  
**Specific Aim 1:**  
 Compare the feasibility and effectiveness of AE

training to a CONT condition at the end of treatment (12 weeks) in VA participants with SCZ or schizoaffective disorder. We predict that the completion of this training will be feasible in our VA population, and that the AE group will exhibit significantly greater improvement on the MCCB than the CONT group.

**Statistical analysis:** Basic statistical comparisons will be performed preliminarily before using a unified statistical approach. Two-sample t-tests using the change in cognitive tests and functional scales as dependent variables will compare AE to CONT participants. The statistical methodology includes both initial descriptive comparisons followed by a more complex unified statistical approach. Spec Aim 1 will ultimately be addressed in a full Merit project using a linear mixed model that is conceptually similar to analysis of variance (ANOVA). However, in this Pilot proposal we will build intuition about the model and the expected results by performing simple comparisons of direct interest prior to complex modeling. To accomplish this preliminary descriptive step and test our hypothesis we will use a univariate analysis of covariance (ANCOVA) looking at change scores with baseline measures plus age, sex, and anticholinergic load as covariates. We predict that greater anticholinergic load of medication will predict poorer improvement. With a sample size of 20 completers per treatment group, we will be sensitive to a within-between interaction effect size of  $f=0.456$  at an alpha level of 0.05 with a power of 0.80. This can be interpreted as a sensitivity to between group difference in change scores of 9.5 MCCB composite t-score units (mean=50, SD=10), which is a meaningful clinical effect.

We will also undertake exploratory (non-inferential) analyses to estimate the strength of association of multiple dependent measures from the cognitive and functional domains. Data reduction via factor analysis will be performed for the MCCB battery data to reduce the number of dependent measures. Because the analysis of this data will employ multiple independent analyses, uncorrected significance tests will not be appropriate for inferential interpretation. However, uncorrected p-values will be reported as arbitrary criteria of effect size strength in deference to widespread use in social science for exploratory analyses.

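### The stated 80% power at an effect size of 0.5 with 20 per group has no metric; as a standardised mean difference, power is about 34%

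*Combined protocol and SAP*

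**What the plan says.** In Sample size determination, the planned effect comes from "studies of AE compared to a control condition in which the effect sizes average approximately 0.5", together with a meta-analysis and other studies of cognitive remediation in schizophrenia, also averaging 0.5. The section then states: "With alpha set at 0.05, an effect size of 0.5 will yield a power of 0.80" for 20 completers per group, with dropouts replaced. It concludes: "This sample size will be adequate to detect significant between group differences in MCCB change scores". It adds: "More importantly for a pilot study, this sample size will allow us to estimate effect sizes specific to the target Veteran population".

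In the Statistical analysis plan under Specific Aim 1, the primary comparison is an ANCOVA "looking at change scores with baseline measures plus age, sex, and anticholinergic load as covariates". Its sensitivity is given separately: "With a sample size of 20 completers per treatment group, we will be sensitive to a within-between interaction effect size of" f = 0.456, at alpha 0.05 and power 0.80. That is translated as follows: "This can be interpreted as a sensitivity to between group difference in change scores of 9.5 MCCB composite t-score units (mean=50, SD=10".

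On the outcome itself, the primary outcome section says "The MCCB has excellent test-retest reliability" but gives no coefficient.

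**The concern.** Two sections describe the same endpoint, sample size, alpha and power, yet one gives the 80%-power effect as 0.5 and the other as f = 0.456. For two equal groups f is half of d, so f = 0.456 is a difference of about 0.9 SD. If 0.5 is a standardised mean difference, the sections differ nearly twofold and the 80% cannot be right.

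What is at stake is how the result is read. Specific Aim 1 predicts a significantly greater improvement with exercise, and the ANCOVA is the test of that prediction. A reader who believes the trial had 80% power for the expected effect will take a non-significant result as evidence against it. If true power is about one in three, such a result says little. The section also says that this pilot will inform the size of a full study, so the scale of its effect sizes needs to be clear.

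**Working it through.** **Inputs from the documents.** 20 completers per group (N = 40); alpha 0.05; claimed power 0.80; effect size 0.5, metric not stated (Sample size determination). ANCOVA on change with four covariates; f = 0.456; 9.5 units; SD 10 (Specific Aim 1). Sidedness is not stated, so two-sided is taken as the main case. Any baseline-to-follow-up correlation r below is an assumption unless marked otherwise.

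**1. Reproduce the Specific Aim 1 figure.** Noncentral F with 1 numerator df, error df = 40 − 2 − 4 = 34, noncentrality f² × N = 0.456² × 40 = 8.32. Power = 0.800. The figure is therefore a two-sided between-group ANCOVA f on the analysed score, and d = 2f = 0.912. Without covariates (df 38), 80% is reached at d = 0.909.

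**2. Read 0.5 as d on the analysed score.** Noncentral t, noncentrality d × √(n/2) = 0.5 × √10 = 1.58.

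| | df 38 | df 34 (ANCOVA) |
|---|---|---|
| Two-sided power | 0.338 | 0.336 |
| One-sided power | 0.463 | 0.462 |

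To reach 80% at d = 0.5 takes 64 per group two-sided, or 51 one-sided. With 20 per group, 80% is reached at d = 0.91 two-sided, or 0.80 one-sided. The smallest observed d that is significant at two-sided 0.05 is t(0.975, 38) × √(2/20) = 2.024 × 0.316 = 0.64, so an observed 0.5 would not be significant.

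**3. Read 0.5 as raw-score SDs, with baseline adjustment.** The effective d is 0.5/√(1 − r²), df 34, two-sided:

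| Assumed r | Effective d | Power |
|---|---|---|
| 0.5 | 0.58 | 0.43 |
| 0.7 | 0.70 | 0.58 |
| 0.8 | 0.83 | 0.73 |
| 0.85 | 0.95 | 0.83 |
| 0.9 | 1.15 | 0.94 |

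80% needs r of about 0.84 (0.78 one-sided). At r = 0.836 and SD 10 the detectable difference is 0.912 × √(1 − 0.836²) × 10 = 5.0 units, whereas Specific Aim 1 says 9.5.

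**4. The correlation implied by Specific Aim 1.** SD of change = 9.5/(2 × 0.456) = 10.42. With a raw SD of 10, r = 1 − (10.42/10)²/2 = 0.46. With SD 10, the largest baseline-adjusted detectable difference (at r = 0) is 0.912 × 10 = 9.1 units, so 9.5 fits unadjusted change scores. At this r, a 5-unit difference has power 0.32 on change scores (5/10.42 = 0.48 SD, df 38) and 0.41 with baseline adjustment (df 34).

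**5. Read 0.5 as Cohen's f.** At df 34, f = 0.5 has noncentrality 0.25 × 40 = 10 and power 0.87; f = 0.456 gives 0.80. But f = 0.5 is d = 1.0.

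**6. Read it as a repeated-measures interaction with f = 0.25 (half of 0.5).** Two time points, noncentrality f² × N × 2/(1 − r), df 38. Power is 0.74, 0.80 and 0.87 at assumed r of 0.3, 0.4 and 0.5. At r = 0.4 the change-score f is 0.25 × √(2/0.6) = 0.456, the Specific Aim 1 value. In raw units that is 2 × 0.456 × √(2 × 0.6) = 1.0 SD.

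**The case against.** The strongest reply is that the 34% depends on a metric the plan never states. Where the plan names a metric for a group comparison, it uses f. On that scale 0.5 gives 0.87, so 20 per group would be enough and 0.80 would be conservative. An interaction f of 0.25 at r = 0.4 even reproduces both the 0.80 and the 0.456. The raw-SD reading is not far-fetched either: baseline is a planned covariate, reliability is called excellent, and an r of 0.85 would give 0.83. The r of 0.46 drawn from the 9.5 units assumes that SD 10 is the trial's raw SD rather than a norm, and that 9.5 is not loosely rounded. Finally, d = 0.91 is a conversion that the plan does not print, and this is a pilot that already discloses f = 0.456.

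Much of this stands. The 34% is conditional, and the plan does not settle which reading was meant. But the f and interaction readings both imply a true difference of about 0.9 to 1.0 SD, and nothing in the plan shows that the source studies' average of 0.5 is on such a scale. The raw-SD reading needs a correlation of about 0.84 and would then put the detectable difference at 5.0 units, against the printed 9.5. The conversion to d = 0.91 is supported because 0.456 reproduces exactly as the planned ANCOVA. Pilot status lowers the consequence but does not make the power sentence correct, and the plan makes the adequacy claim without qualification.

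**Conclusion.** The concern holds. The power statement cannot be reproduced as written, and on its natural reading it conflicts with Specific Aim 1. If 0.5 is a standardised mean difference on the analysed score, power is 0.34 two-sided (0.46 one-sided) rather than 0.80, and the 80%-power effect is d = 0.91. If it is in raw SDs with baseline adjustment, power runs from 0.43 to 0.94 over assumed correlations of 0.5 to 0.9. If it is Cohen's f, power is 0.87. No reading that rests on a stated assumption gives 80% power for a standardised difference of 0.5.

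This should be fixed, but the practical harm is modest: estimation is put first, and Specific Aim 1 already shows the larger detectable effect. The remaining risks are that a null primary test is over-interpreted and that an effect size without a metric is carried into the full study.

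**What to change.** In Sample size determination, state the metric, SD, sidedness and any assumed baseline correlation behind the 0.5. Then, according to what was meant:

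- **Standardised mean difference:** replace the power sentence with wording such as: *With 20 completers per group and two-sided alpha 0.05, 80% power is reached at d = 0.91 (f = 0.456); power for a standardised difference of 0.5 is about 0.34.* Delete or qualify the sentence claiming that the sample is adequate to detect a significant difference.
- **Raw-score SDs with baseline adjustment:** state the correlation and its basis, and recompute both sections from it.
- **Cohen's f or an interaction effect:** say so, and give the equivalent difference in MCCB T-score units.

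Two smaller clarifications belong with this. Under Specific Aim 1, label f = 0.456 as the ANCOVA change-score f and state the SD of change behind 9.5 units (about 10.4; with an SD of 10 the figure is 9.1). Under Specific Aim 3, explain why the UPSA sensitivity is f = 0.481 for a similar ANCOVA at the same sample size, where 0.481 gives power 0.84 rather than 0.80.

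The cost is wording only. The stated power may look less favourable; enrolment, conduct and analysis do not change.

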See Table 3 for **Timeline**. We will track the attendance of each participant, and will call to ascertain the reasons for missed sessions. Reasons will be compiled as pilot data for planning a larger study.

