To assess feasibility we will collect data on the numbers of SCZ participants who are potentially interested in participation, the number who screen out and for what reasons, the number of drop outs, and the reasons for their dropping out. We will also collect data on attendance and barriers to attendance. For these measures we will compute descriptive statistics. These data will inform proposals for fully powered future studies.

**Specific Aim 2:** Evaluate whether increases in cardiovascular fitness ( $VO_2\text{max}$ ) mediates cognitive improvement. We predict that the degree of estimated  $VO_2\text{max}$  improvement in the AE group will predict the degree of cognitive improvement with training.

**Statistical analysis:** We will assess potential mediator effects of  $VO_2\text{max}$  as well as potential moderator effects of age, sex, and anticholinergic load to better formulate covariates in future models. The association between potential moderators and cognitive improvement will be evaluated through use of bivariate and multiple correlations; only significant associations will be further assessed as possible moderators. The assessment of  $VO_2\text{max}$  as a potential mediator will be evaluated using partial correlation coefficients from the regression model. With a total sample size of 20 participants in the treatment group, we will be sensitive to a bivariate effect size of  $r = 0.428$  at an alpha level of 0.05 with a power of 0.80. This would allow us to detect differences of up to 18% in potential moderator variables. In a multiple regression with four predictor variables (because of issues of multicollinearity with anticipated high degrees of correlation possible between the potential moderator variables, it is doubtful that we will have a viable model with more than four predictors), we will be sensitive to an overall effect size of  $f^2 = 0.063$ . Although sensitivity is provided, we consider the analyses used in the evaluation of this pilot data to be focused on estimation of effect sizes for future studies rather than for inferential interpretation. Because of this, p-values (and criterion alpha levels) will not be corrected for multiple independent testing. We will also run an exploratory regression model with mean training hours per week.

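### The primary MCCB comparison is sized on completers with dropouts replaced, but the plan neither defines a completer nor provides for assessing and analysing people who stop training

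*Combined protocol and SAP*

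**What the plan says.** Sample size determination gives power for a "planned sample size of 20 completers per treatment group (with dropouts replaced". It allows for about 25% dropout, introduced with "We estimate liberally from our prior work (cognitive remediation study", and concludes "so we will need to recruit 53 subjects in order to obtain the 40 completers needed for analysis". The Aim 1 statistical analysis repeats the basis: "With a sample size of 20 completers per treatment group".

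The Aim 1 test is an ANCOVA on change scores, which needs a Day 84 MCCB from each person analysed. No analysis set and no missing-data rule are given. The repeated-measures alternative is put off: "Spec Aim 1 will ultimately be addressed in a full Merit project using a linear mixed model".

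For feasibility, the plan records "the number who screen out and for what reasons, the number of drop outs, and the reasons for their dropping out", together with attendance, and adds "For these measures we will compute descriptive statistics". Staff track attendance and "will call to ascertain the reasons for missed sessions". The visit schedule places randomisation in the Screen/Baseline column and the MCCB at Day 84 and at the 8-week follow-up (week 20). It does not say whether those visits take place for someone who has stopped training.

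The recruitment total is not consistent. It is 53 under Sample size determination, but 40 under Risks to Subjects (Human Subject Involvement and Characteristics) and in the Targeted/Planned Enrollment Table.

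**The concern.** Randomisation comes before training, and screen-outs are counted separately from dropouts. The dropouts are therefore most naturally people lost after randomisation, although the documents do not say so outright. Replacing them restores the number analysed but not the randomised comparison.

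*Completer* could mean someone who finished training, in which case people with a Day 84 MCCB might be left out. It could also mean someone with a Day 84 MCCB, in which case the set is the observed cases. With no definition, the choice could be made after the data are seen.

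This matters because the plan says the more important use of the pilot is an effect size for planning a full trial, and Aim 1 also tests a hypothesis. A completer estimate answers a different question from the effect of being assigned to AE, and any selection in it would carry into the next trial's sample size.

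**Working it through.** **1. The plan's own figure.** 40 / (1 − 0.25) = 53.3, so 53 reproduces to rounding. About 53 − 40 = 13 recruited people would not be in the analysis. With the lab's retention in its cognitive training study (85% under Preliminary Studies, 83% under Potential challenges), 40/0.85 = 47.1 and 40/0.83 = 48.2, so 7 to 8 would be left out. If 40 is the enrolled total, 25% loss leaves 30. The 82.5% figure from the exercise lab is not used: Potential challenges calls it retention, but Preliminary Studies calls it attendance.

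**2. Bias model.** All inputs here are assumptions; the documents give neither dropout by arm nor its relation to outcome. Assume no true effect. Those lowest on a latent tendency to stay drop out, and MCCB change has correlation ρ with that tendency (after covariates). In an arm with dropout d, mean change among those retained, in SD of change, is

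m(d) = ρ·φ(z)/(1 − d), with z = Φ⁻¹(d).

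The values of φ(z)/(1 − d) are 0.195 (d = 10%), 0.274 (15%), 0.350 (20%), 0.424 (25%), 0.497 (30%) and 0.644 (40%). Bias is m for AE minus m for CONT.

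| Dropout AE/CONT | ρ = 0.3 | ρ = 0.5 |
|---|---|---|
| 25/25, same relation | 0 | 0 |
| 20/15 | 0.023 | 0.038 |
| 30/20 | 0.044 | 0.073 |
| 20/30 | −0.044 | −0.073 |
| 25/25, informative in AE only | 0.127 | 0.212 |
| 40/10 | 0.135 | 0.224 |

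**3. Scale.** The standard error of the difference with 40 analysed is √(4/40) = 0.316 SD. Under no effect, a bias of 0.10 SD would raise two-sided rejection from 5% to about 6.1%, and 0.20 SD to about 9.5%.

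**4. What assessing people who stop would do.** If a random fraction f of them return for Day 84, m becomes ρ·φ(z)(1 − f)/((1 − d) + f·d). At f = 0.5, the 40/10 case falls from 0.135–0.224 to 0.045–0.075, and the 30/20 case to 0.015–0.024. At f = 1 the bias is 0.

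**5. Price in precision.** Take 25% stopping and 53 randomised. If all return, the SE is √(4/53) = 0.275. If those who stop gain none or half of the completer effect, the estimate is 0.75 or 0.875 of it. Effect/SE relative to completers is then 0.75 × 0.316/0.275 = 0.86, or 0.875 × 0.316/0.275 = 1.01. If half return (N about 46.5, SE 0.293), the retained effect is 0.857 or 0.929, and the ratio is 0.92 or 1.00.

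**The case against.** The strongest reply is that both mentions of completers are sample-size statements. The ANCOVA text excludes nobody, and the schedule lists the Day 84 MCCB without conditions. This stands in part. A reader might infer that the plan explicitly orders a completers-only analysis, and it does not. But calling the 40 completers those needed for analysis, replacing dropouts and using dropout data only descriptively all point that way, and nothing points the other way.

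A reader might also infer that selective loss could never be examined. That goes too far. Baseline MCCB and UPSA, PANSS at Days 28 and 56, attendance and dropout reasons allow leavers and stayers to be compared by arm, and allow adjustment if loss depends on those measures. Only loss that depends on the unseen Day 84 score is beyond checking.

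Finally, sampling error is larger than the bias in every scenario above, and contact hours and adherence support are the same in both arms. This also stands, and it rules out inferring that a large bias in favour of AE is expected. On the other side, item (c) of Potential challenges itself foresees that some participants may not tolerate AE, so arm-specific loss is not far-fetched. The standard error is also visible to the reader of the results, whereas selection bias is not.

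**Conclusion.** The point holds as a gap that should be closed. The plan sizes its primary comparison on an undefined completer group with replacement, and does not say that people who stop training are assessed at Day 84 or analysed as randomised. Followed in its natural sense, it gives a comparison open to selection bias.

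The size and direction cannot be known from the documents. Under ρ of 0.3 to 0.5, with poorer improvers leaving, the bias is about 0.02 to 0.07 SD at 20%/15% to 30%/20% dropout. It reaches 0.13 to 0.22 SD only at 40%/10%, or with dropout informative in AE alone. It changes sign if CONT loses more. It is zero if dropout is unrelated to change given the covariates, or if rate and relation are the same in both arms. The standard error is about 0.32 SD. The case for change rests on the low cost of preventing the problem, not on a large expected bias.

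**What to change.** Add to the analysis plan:

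*Participants who stop training are still invited to the scheduled Day 84 and week-20 assessments. The primary analysis is the planned ANCOVA, by assigned arm, on every randomised participant with a Day 84 MCCB, regardless of training completion. Replacements add to, and do not substitute for, those already randomised. A completer analysis, with completer defined in advance, is secondary. Numbers missing Day 84, with reasons, are reported by arm.*

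Reconcile the recruitment total of 53 with the 40 given in the human-subjects section and the enrolment table.

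The cost is small. At most about 13 people are invited to two visits already in the schedule, and staff already telephone about missed sessions. Recruitment need not go beyond 53. There are two downsides. The estimate is diluted by people who stopped, with effect/SE about 0.86 to 1.01 of the completer value at 25% stopping if all return. Some bias also remains if not all return, because the primary set is still those observed at Day 84.
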